#### 8.1 Efficacy Assessments and Procedures

Not applicable.

## 8.2 Safety Assessments and Procedures

The safety profile of the study intervention will be assessed through the recording, reporting and analysis of baseline medical conditions, AEs, physical examination findings, vital signs, electrocardiograms, and laboratory tests.

Comprehensive assessment of any potential toxicity experienced by each participant will be conducted starting when the participants give informed consent and throughout the study. The Investigator will report any AEs, whether observed by the Investigator or reported by the participant; the reporting period is specified in [Section 8.3](#).

### 8.2.1 Physical Examinations

- A complete physical examination will include, at a minimum, assessments of the cardiovascular, respiratory, gastrointestinal and neurological systems.
- A brief physical examination will include, at a minimum, assessments of the skin, lungs, cardiovascular system, and abdomen (liver and spleen).
- Investigators will pay special attention to clinical signs related to previous serious illnesses.

### 8.2.2 Vital Signs

- Vital signs will be measured in supine position.
  - Blood pressure and participant's position during measurement; pulse; respiratory rate; temperature and location of measurement, weight, and height (at Baseline only) will be measured and recorded.
  - Blood pressure and pulse measurements will be preceded by at least 5 minutes of rest for the participant in a quiet setting without distractions (e.g., television, cell phones) and measured with an automated device. Manual techniques will be used only if an automated device is not available.
  - Vital signs (to be taken before blood collection for laboratory tests) will consist of 1 pulse and 1 blood pressure measurement.

### 8.2.3 Electrocardiograms

- Single 12-lead ECG will be obtained as outlined in the SoA using an ECG machine that automatically calculates the heart rate and measures PR, RR, QRS, QT, and QTcF intervals.
- Triplicate ECGs are required when abnormal ECG results are measured. If ECG parameters fall outside of clinical reference range, including QTcF > 450 ms, a repeat ECG is done. When triplicate ECGs are required, 3 individual ECG tracings will be obtained as closely as possible in succession, but no more than 2 minutes apart. The full set of triplicates will be completed in less than 4 minutes and will occur in a resting state without prior procedure such as blood draw. Triplicate measurements can be performed

based on Investigators discretion. When measured as triplicate, the average values will be considered. Additional ECGs during the course of the study will be at the discretion of the Investigator.

#### 8.2.4 Clinical Safety Laboratory Tests

- Blood and urine samples will be collected for the clinical laboratory tests listed in [Appendix 5 Clinical Laboratory Tests](#) at the timepoints listed in the SoA. All samples will be clearly identified. The samples for scheduled laboratory tests will be collected in a fasted state. Participants will refrain from food and fluid with the exception of water for at least 10 hours prior to collection. Unscheduled tests may not require a fasted condition.
- Additional tests may be performed at any time during the study, as determined necessary by the Investigator or required by local regulations.
- The tests will be performed by the local laboratories.
- The Sponsor will receive a list of the local laboratory normal ranges before shipment of study intervention(s). Any changes to the ranges during the study will be forwarded to the Sponsor.
- The Investigator will review each laboratory report, document this review, and record any clinically significant changes occurring during the study as an AE, unless it does not meet the AE definition, as specified in [Appendix 4](#). The laboratory reports will be filed with the source documents.
- Additional serum or highly sensitive urine pregnancy tests may be conducted, as determined necessary by the Investigators or required by local regulation, to establish the absence of pregnancy at any time during the study. To confirm postmenopausal status, FSH will be assessed at Screening only.

#### 8.3 Adverse Events, Serious Adverse Events, and Other Safety Reporting

- The definitions of an AE and SAE are in [Appendix 4](#).
- The Investigator and any qualified designees (e.g., Subinvestigators) are responsible for detecting, documenting, and recording events that meet the definition of an AE or SAE. The Investigator remains responsible for following up AEs that are serious, considered related to the study intervention or study procedures, or that caused the participant to discontinue the study intervention or study, as specified in [Section 8.3.2](#).
- Requests for follow-up will usually be made via the Sponsor or Clinical Research Organization-designated study team member, although in exceptional circumstances the global patient safety department may contact the Investigator directly to obtain further information or to discuss the event.
- The method of recording, evaluating, and assessing causality of AEs and SAEs and the procedures for completing and transmitting SAE reports are in [Appendix 4](#).

- All AEs and SAEs will be collected from the signing of the ICF until the follow-up phone call at the timepoints specified in the SoA ([Section 1.3](#)). Beyond this reporting period, any new unsolicited SAEs that the Investigator spontaneously reports to the Sponsor will be collected and processed.
- All SAEs will be recorded and reported to the Sponsor or designee immediately and under no circumstance will this exceed 24 hours, as indicated in [Appendix 4](#). The Investigator will submit any updated SAE data to the Sponsor within 24 hours of it being available using the same procedure that was used for the initial report.
- Investigators are not obligated to actively solicit information on AEs or SAEs after the end of study participation. However, if the Investigator learns of any SAE, including a death, at any time after a participant has been discharged from the study, and he/she considers the event to be reasonably related to the study intervention or study participation, the Investigator will promptly notify the Sponsor.

### **8.3.1                   Method of Detecting Adverse Events and Serious Adverse Events**

At each study visit, the participant will be queried on changes in his or her condition.

Care will be taken not to introduce bias when detecting AEs and/or SAEs. Open-ended and nonleading verbal questioning of the participant is the preferred method to inquire about AE occurrences.

The method of recording, evaluating, and assessing causality of AEs and SAEs and the procedures for completing and transmitting SAE reports are in [Appendix 4](#).

### **8.3.2                   Follow-up of Adverse Events and Serious Adverse Events**

After the initial AE/SAE report, the Investigator is required to proactively follow each participant at subsequent visits/contacts. All SAEs will be followed until resolution, stabilization, the event is otherwise explained, or the participant is lost to follow-up (as defined in [Section 7.3](#)). Reasonable attempts to obtain this information will be made and documented. It is also the Investigator's responsibility to ensure that any necessary additional therapeutic measures and follow-up procedures are performed. Further information on follow-up procedures is in [Appendix 4](#).

### **8.3.3                   Regulatory Reporting Requirements for Serious Adverse Events**

- Prompt notification by the Investigator to the Sponsor of an SAE (particularly life-threatening and deaths) is essential so that legal obligations and ethical responsibilities toward the safety of participants and the safety of a study intervention under clinical investigation are met.
- The Sponsor has a legal responsibility to notify both the local regulatory authority and other regulatory agencies about the safety of a study intervention under clinical

investigation. The Sponsor will comply with country-specific regulatory requirements relating to safety reporting to the regulatory authority, IRB/IEC, and Investigators.

- Individual Case Safety Reports will be prepared for SUSARs according to local regulatory requirements and Sponsor policy and forwarded to Investigators within 15 days.
- An Investigator who receives an Individual Case Safety Report describing a SUSAR or other specific safety information (e.g., Emerging Safety Issue Report, summary or listing of SAEs/SUSARs) from the Sponsor will read it and confirm completion of this activity. This information will be filed in the Investigator's Site File, and the IRB/IEC will be notified, if appropriate, according to applicable local laws/regulations and site SOPs.

[figure not shown]
#### 8.3.4      **Pregnancy**

- Details of all pregnancies in female participants and female partners of male participants will be collected after the start of study intervention and until 6 months after the last administration of study intervention.
- If a pregnancy is reported, the Investigator will record the pregnancy information on the appropriate form and submit it to the Sponsor within 24 hours of learning of the pregnancy.
- While pregnancy itself is not considered to be an AE or SAE, any pregnancy complication or elective termination of a pregnancy will be reported as an AE or SAE. Adverse pregnancy outcomes (e.g., spontaneous abortion, fetal death, stillbirth, congenital anomalies, ectopic pregnancy) are considered and reported as SAEs. A spontaneous abortion (occurring at < 22 weeks gestational age) or stillbirth (occurring at > 22 weeks gestational age) is always considered to be an SAE and will be reported as such.
- The participant/pregnant female partner will be followed to determine the outcome of the pregnancy. The Investigator will collect follow-up information on the participant/pregnant female partner and the neonate, and the information will be forwarded to the Sponsor. Generally, follow-up will not be required for longer than 6 to 8 weeks beyond the estimated delivery date for a healthy newborn. In case of a congenital anomaly or other illness of the newborn, follow-up will continue until the illness has resolved or there is a definite outcome of the event.
- Any post study pregnancy related SAE considered reasonably related to the study intervention by the Investigator will be reported to the Sponsor as specified in **Section 8.3.3**. While the Investigator is not obligated to actively seek this information in former study participants/pregnant female partner, he or she may learn of an SAE through spontaneous reporting.
- Any female participant who becomes pregnant while participating in the study will discontinue study intervention or be withdrawn from the study.

- Abnormal pregnancy outcomes (e.g., spontaneous abortion, fetal death, stillbirth, congenital anomalies, ectopic pregnancy) are considered SAEs.

### 8.3.5 Adverse Events of Special Interest

An AESI is a noteworthy event of the particular study treatments that can be appropriate to monitor closely. **CCI**

## 8.4 Pharmacokinetics

### 8.4.1 Blood Sampling and Bioanalysis

- Samples are collected only where allowed by local law/regulations.
- The actual date and time (24-hour clock time) of:
  - Each sample collection

- Study intervention administration prior to sample collection will be recorded in the eCRF to determine the elapsed time of sampling in relation to the administration of study intervention.
- Whole blood samples of approximately 2 mL per PK sample collection time point will be collected for measurement of plasma concentrations of xevinapant and its metabolite D-1143-MET1. Collection times are specified in the SoA. The actual date and time (24-hour clock time) of each sample will be recorded to calculate actual time elapsed since the prior dose administration. The sampling timing may be altered during the study based on newly available data (e.g., to obtain data closer to the time of peak plasma concentrations) to ensure appropriate monitoring.
- The quantification of xevinapant and D-1143-MET1 in plasma will be performed using a validated assay method.
- Concentrations will be used to evaluate the PK of xevinapant and its metabolite D-1143-MET1.
- Remaining samples collected for bioanalytical measurements may also be used for CCI [REDACTED] t of metabolites of xevinapant or CCI [REDACTED] biomarkers during or after the study. Retention time and possible analyses of samples after the end of study are specified in the respective ICF.
- Details on processes for collection and handling of these samples are in the Laboratory Manual.
- For details on PK sampling, refer to the SoA in [Section 1.3](#).

#### 8.4.2 PK Parameters

- PK parameters will be derived using noncompartmental methods with the validated computer program Phoenix® WinNonlin® (version 6.4 or higher; Certara, L.P., Princeton, New Jersey, USA). SAS version 9.4 or higher will be used to calculate metabolic ratios.
- Concentration data may be used for integrated data analyses across studies and reported separately from the main CSR.
- The following PK parameters for xevinapant and its metabolite D-1143-MET1 will be calculated from individual plasma concentration-time data for xevinapant and its metabolite(s), when appropriate:

Other PK parameters may be calculated if appropriate. Details will be in the IAP.

Symbol	Definition
AUC 0-tlast	The area under the concentration-time curve (AUC) from time zero (= dosing time) to the last sampling time ( $t_{last}$ ) at which the concentration is at or above the lower limit of quantification. Calculated using the mixed log-linear trapezoidal rule (linear up, log down).
AUC 0-∞	The AUC from time zero (dosing time) extrapolated to infinity, based on the predicted value for the concentration at $t_{last}$ , as estimated using the linear regression from $\lambda_z$ determination. $AUC_{0-∞} = AUC_{0-t_{last}} + C_{last\ pred} / \lambda_z$
AUC 0-24	The AUC from time zero (= dosing time) to 24 hours

Symbol	Definition
AUC extra%	The AUC from time $t_{last}$ extrapolated to infinity given as percentage of AUC 0-∞ . $AUC_{extra} = (\text{extrapolated area}/AUC_{0-∞}) * 100$ .
CL/F	The apparent total body clearance of study intervention following extravascular administration. $CL/F = \text{Dose}_{p.o.}/AUC_{0-∞}$ .
C max	Maximum observed concentration
t max	The time to reach the maximum observed concentration collected during a dosing interval (unless otherwise defined, take the 1 st occurrence in case of multiple/identical C max values)
t 1/2	Apparent terminal half-life. $t_{1/2} = \ln(2)/\lambda_z$
λ z	Terminal first order (elimination) rate constant. Determined from the terminal slope of the log-transformed concentration curve using linear regression on terminal data points of the curve.
V z /F	The apparent volume of distribution during the terminal phase following extravascular administration. $V_z/F = \text{Dose}/(AUC_{0-∞} * \lambda_z)$ following single dose.

The exact date/time of sample collection and study intervention (24-hour clock time) must be recorded in the eCRF and will be used in the calculation of PK parameters. The accepted time deviations from planned PK times that will not be considered a protocol violation are listed below:

Procedure	Time Point (Relative Time)	Window Allowance
Pharmacokinetics	Predose	- 90 min
	0.5 to 2 hours postdose	- / + 2 min
	> 2 to 12 hours postdose	- / + 5 min
	> 12 to 72 hours postdose	- / + 15 min

## 8.6 Biomarkers

Not applicable.

## 8.7 Immunogenicity Assessments

Not applicable.

## 8.8 Health Economics

Healthcare resource utilization data are not collected in this study.

## 9 Statistical Considerations

### 9.1 Statistical Hypotheses

No formal statistical hypothesis will be tested, as the study is designed to be exploratory.

### 9.2 Sample Size Determination

A maximum of 32 East Asian participants will be assigned to study intervention such that approximately 20 evaluable participants (at least 10 Japanese) complete the study.

Although no hypothesis tests will be performed, the sample size of the study should be sufficient to estimate the PK parameters in Japanese (Group 1) and non-Japanese East Asian (Group 2) participants with adequate precision.

PK data collected in studies in healthy Caucasian participants suggests that the total variability of  $AUC_{0-tlast}$ ,  $AUC_{0-\infty}$  and  $C_{max}$  is moderate to high, with a geometric CV ranging from 30% to 40% (refer to IB Version 14). Based on these data a sample size of 10 participants per group is considered sufficient to estimate PK parameters of xevinapant in Japanese, non-Japanese East Asian and in all East Asian participants.

In addition, the ratio of PK parameters between the ethnic categories in Group 1 versus Group 2 may also be estimated. Assuming CV (%) of 35% for PK parameters of xevinapant, the precision for the estimated PK parameters ratio to be achieved with a given number of evaluable participants is summarized in [Table 1](#) if 20 evaluable participants are included in this study (10 per group), and the observed ratio is 1.0, then the 90% CI for the ratio will, with 80% probability, be contained in 0.7435 to 1.3451. A further increase in sample size does not substantially improve the precision. On the other hand, even with a slightly smaller number of completed participants, the precision will not be markedly decreased.

Therefore, 24 participants (12 per group) will be initially assigned to study intervention such that approximately 10 evaluable participants per group complete the study, allowing for a 17% drop-out rate. If the number of completers is less than 10 in one group, then up to 4 additional participants may be included in each group (up to 32 participants in total).

**Table 1** 90% CI with 80% tolerance probability

N1	N2	CV = 30%	CV = 35%	CV = 40%
8	8	0.7450-1.3423	0.7112-1.4062	0.6796-1.4715
10	10	0.7741-1.2917	0.7435-1.3451	0.7147-1.3993
12	12	0.7951-1.2577	0.7668-1.3040	0.7402-1.3510

CI = confidence internal; CV = coefficient of variation.

Calculations performed in R version 4.0.1.

Assumption of N1 = N2 = 10 is based on total number of Japanese and non-Japanese East Asian participants per group targeted for this study.

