**Number of Participants:** 24 participants (12 per group) will be initially assigned to study intervention such that approximately 10 evaluable participants per group complete the study.

**Study Intervention Groups and Duration:** Group 1 will enroll at least 10 Japanese participants. Group 2 will enroll at least 10 non-Japanese East Asian participants. East Asia includes Korea or Greater China. The planned total duration of the study for each participant will be approximately 5 weeks, including an up to 4-week Screening Period, an In-house Period at the CRU (Day -1 to Day 4), and a Safety Follow-up on Day 8.

**Data and Safety Monitoring /Other Committee:** No

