### 1.3

### Schedule of Activities

Assessments & Procedures	Screening	Admission to CRU					SFU (Televisit)	Notes
Study Day	-28 to -3	-1	1	2	3	4 (EoT)	8 (-1 / +2 days)	
Written informed consent	X							Informed consent to be available before start of any study specific assessments.
Participants resident at CRU		X	X	X	X	X		Admission to CRU in the afternoon on Day -1 until discharge on Day 4 after completion of all study-related activities
Inclusion and exclusion criteria	X	X						Recheck clinical status before administration
Demography	X							Including age (year of birth), sex, race and ethnicity
Full physical examination	X	X				X		
Medical history	X							
Pregnancy test	X	X				X		Pregnancy test using serum (at Screening) and using urine (on Day -1 and End of Study), to confirm non-pregnant status (females only)
Follicle stimulating hormone	X							To confirm postmenopausal status (females only)
Serology	X							HIV, hepatitis B and C SARS-CoV-2
Drug and alcohol screen	X	X						
Clinical laboratory tests a	X	X	X	X		X		After at least 10 hours fasting, Day 1 sampling is predose
Safety 12-Lead ECG	X		X	X		X		Day 1: predose, 1 hour postdose, Day 2 (24 hours postdose), and Day 4 (72 hours postdose) (see Section 8.2.3 for further details)

Assessments & Procedures	Screening	Admission to CRU					SFU (Televisit)	Notes
		-1	1	2	3	4 (EoT)		
Study Day	-28 to -3	-1	1	2	3	4 (EoT)	8 (-1 / +2 days)	
Vital signs	X	X	X	X	X	X		Height and Weight to be collected at Screening only. Day 1: predose, 1, 2, 4, 12 hours; Day 2: 24 hours, Day 3: 48 hours, Day 4: 72 hours
CCI								
Study intervention			X					
AE & SAE review	X	X	X	X	X	X	X	
Concomitant medications review	X	X	X	X	X	X	X	
PK blood sampling (plasma)			X	X	X	X		Day 1: predose, and 0.25, 0.5, 1.0, 1.5, 2, 2.5, 3, 4, 6, 8, and 12 hours postdose; Day 2: 24 and 36 hours postdose; Day 3: 48 hours postdose, Day 4: 72 hours postdose. See Section 8.4 for collection windows and further details. The time and date of each collection to be recorded in eCRF.

aUrine samples will be collected at Screening and times of other clinical labs.

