#### **4.4 End of Study Definition**

The end of the study is defined as the date of the last visit of the last participant or the last scheduled procedure shown in [Section 1.3](#).

A participant has completed the study if he/she has completed all study parts, including the last visit or the last scheduled procedure shown in [Section 1.3](#).

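### Does the top-up rule in Protocol 9.2 count the wrong participants and open dosing in a group that is not short?

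*Protocol*

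**What the plan says.** Protocol 9.2 opens with a ceiling of 32 assigned participants, "such that approximately 20 evaluable participants (at least 10 Japanese) complete the study". The Synopsis and the last paragraph of 9.2 give the per-group form: 24 participants, 12 per group, "such that approximately 10 evaluable participants per group complete the study". Table 1 is introduced as precision by number of evaluable participants.

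The top-up rule follows directly: "If the number of completers is less than 10 in one group, then up to 4 additional participants may be included in each group", with 32 as the total.

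The same section comments on precision in both directions. On more participants: "A further increase in sample size does not substantially improve the precision". On fewer: "even with a slightly smaller number of completed participants, the precision will not be markedly decreased". Protocol 9.1 adds: "No formal statistical hypothesis will be tested, as the study is designed to be exploratory".

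Protocol 4.4 defines completion by visits and procedures: "A participant has completed the study if he/she has completed all study parts, including the last visit or the last scheduled procedure". Neither document defines evaluable.

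**The concern.** Two things look wrong.

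**The unit changes.** The target and Table 1 count evaluable participants; the trigger counts completers. The two counts can differ in both directions.
- A completer can lose PK data. SAP 10.2.1 lists vomiting, dosing errors and sample processing errors among events that may lead to exclusion of values. SAP 16.1.4.1 removes from PK evaluation anyone whose predose value exceeds 5% of Cmax. Such a person would not count towards a literal trigger.
- PK sampling ends on Day 4 ("Day 3: 48 hours postdose, Day 4: 72 hours postdose"), but the last contact is the Day 8 televisit. Someone with a full 72-hour profile who misses that call might not be a completer, so the rule could permit a replacement that the PK analysis does not need.

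**The scope widens.** A shortfall in one group appears to permit four more participants in each group. Extra participants in the full group cannot improve the short group's own geometric mean.

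At stake is whether healthy volunteers are dosed for little purpose, when Protocol 2.3 asks for risk to be minimized because they gain nothing from exposure, and whether a group could end below 10 evaluable without a top-up.

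**Working it through.** **Inputs.** From Protocol 9.2: CV 35%, 90% CI, 80% tolerance probability, observed ratio 1.0, 12 assigned and 10 evaluable per group, 17% drop-out, cap of 32. From SAP 16.1.2: a 95% CI for each geometric mean. Other drop-out rates and all PK-loss rates below are assumptions, and losses are taken as independent.

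**1. Reproduce Table 1.** With s = sqrt(ln(1 + CV²)) and df = n1 + n2 − 2,

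limits = exp(± t(0.95, df) × s × sqrt(χ²(0.80, df)/df) × sqrt(1/n1 + 1/n2)).

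For 10 v 10 at CV 35%: s = 0.3399, t = 1.7341, sqrt(22.7595/18) = 1.1245, sqrt(0.2) = 0.4472. The half-width is 0.2964 and the limits are 0.7435 to 1.3451, as stated. All nine cells of Table 1 reproduce to four decimals. The cap also adds up: 24 + 4 + 4 = 32.

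**2. Cost of an unrepaired shortfall (CV 35%).**

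| Evaluable | Limits for the ratio |
|---|---|
| 10 v 10 (plan) | 0.7435–1.3451 |
| 9 v 10 | 0.7361–1.3585 |
| 8 v 10 | 0.7273–1.3749 |
| 9 v 12 | 0.7477–1.3374 |

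Nine against a full group of 12 is already slightly tighter than the planned 10 v 10. For one group's geometric mean, using the one-sample form exp(t(0.975, n−1) × s × sqrt(χ²(0.80, n−1)/(n−1))/sqrt(n)), the 95% CI factor is 1.328 at n = 10 and 1.359 at n = 9.

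**3. How often could a literal trigger miss a shortfall?** Per group, the chance of at least 10 completers but fewer than 10 evaluable is the sum over c = 10 to 12 of Binom(c; 12, 1−d) × P(Binom(c, 1−p) ≤ 9), where d is drop-out and p is PK loss among completers.

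The documents give one anchor for p. Protocol 2.3 does not list vomiting among the more frequent events in 58 healthy participants and says every other event occurred in a single participant, so vomiting was at most 1/58 = 1.7%. The 5% row has no source and only shows sensitivity.

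| p | d = 0% | d = 2% | d = 5% | d = 17% |
|---|---|---|---|---|
| 0 | 0 | 0 | 0 | 0 |
| 1/58 | 0.1% | 0.7% | 2.1% | 5.1% |
| 5% (assumed) | 2.0% | 4.4% | 8.5% | 14.8% |

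In the rows with p above zero, 80% to 96% of these shortfalls are by exactly one person, which is the 9 v 10 case in step 2.

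**4. How often could the each-group wording matter?** With q = P(Binom(12, 1−d) ≤ 9), the chance that exactly one group is short is 2q(1−q).

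| d | q | Any group short | Exactly one short |
|---|---|---|---|
| 2% | 0.0015 | 0.3% | 0.3% |
| 5% | 0.0196 | 3.9% | 3.8% |
| 10% | 0.1109 | 20.9% | 19.7% |
| 17% | 0.3344 | 55.7% | 44.5% |

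In that event the literal rule permits 24 + 4 + 4 = 32 dosed; a top-up of the short group alone permits 24 + 4 = 28.

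**5. What would four more in a full group buy?** Moving from 10 v 12 to 10 v 16 takes the ratio limits from 0.7551–1.3243 to 0.7709–1.2971. The 95% CI factor for all East Asian participants goes from 1.183 (n = 22) to 1.164 (n = 26); at the planned n = 20 it is 1.195. The gain is modest, in line with the comment in 9.2, but not zero, and the East Asian population as a whole is part of the primary objective.

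**The case for a change.** The best case for rewording is that the sentence governs dosing of people who cannot benefit, that a few words would tie it to the group that is short, and that it matters most in the usual pattern: once a top-up is triggered, only one group is short in 80% of cases at 17% drop-out and 99% at 5%. If the sponsor means the harmless reading, the rewording merely states it.

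Part of this stands. Read literally, the sentence does open enrolment in both groups, and limiting it to the short group would be tidier. But the 80% and 99% are conditional on a trigger; at 5% drop-out exactly one group is short in only 3.8% of trials.

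The other half, replacing completers by a PK-evaluable trigger, is not a clean improvement. It introduces a term that neither document defines. It drops completion from a target that asks for both evaluability and completion. It would also still miss losses found only at bioanalysis or at the data review meeting, where Protocol 9.3 places final exclusions. The route to losing a completer is narrow in any case: the PK analysis set needs one valid postdose measurement, dosing is supervised with a mouth check (Protocol 6.4), there are 15 postdose samples, and SAP 10.2.1 foresees case-by-case review rather than automatic removal.

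**Conclusion.** No change follows. No figure in 9.2 is wrong. The word completers comes immediately after a sentence about evaluable participants who complete, and 9.2 itself discusses precision in terms of completed participants, so the shorthand reading is the natural one. The phrase about each group works as a per-group limit that adds up to the stated 32.

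Even on the literal reading the results stay sound. The top-up is optional, and 9.2 accepts slightly fewer participants. SAP 16.1.5 plans no formal PK analysis, and the between-group ratio is only something that may be estimated. The cost of one missing evaluable participant is an upper limit of 1.359 instead of 1.345. The possible excess is four participants, and only if the sponsor chooses to enrol them in a group that already has enough.

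These sizes rest on CV 35%, independent drop-out and the assumed loss rates. At CV 40%, 9 v 10 gives 0.7067–1.4151 against 0.7147–1.3993, which leads to the same conclusion. The each-group phrase is an editorial matter at most.
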